1.3 Research to be carried out.

In this review, cachexia is a common complication of various advanced malignant tumors, which seriously affects the quality of life and survival time of patients. In view of the clinical problem of non-nutritional response in patients with cachexia, we plan to carry out a clinical case-control study on the intervention of creatine combined with curcumin in patients with cachexia. Overall, we limited the study subjects to upper digestive tract tumors and diagnosed patients with early cachexia. The main purpose of this study is to determine whether the combination of the two can play a positive and stable role in inhibiting the inflammation of cachexia and improving metabolic status, so that basic nutrition can play a role, to reduce the level of skeletal muscle consumption, maintain weight, improve quality of

life, save medical costs, and extend survival time.

2. Purpose of the study

(1) To investigate whether creatine combined with curcumin can improve the inflammatory state, correct the disorder of nutrient metabolism and improve the nutritional status in the early cachexia stage of upper gastrointestinal neoplasms.

(2) To investigate whether creatine combined with curcumin can improve the quality of life and prognosis of patients with early cachexia in upper digestive tract tumors.

3. Study design type, principle, and test procedure

(1) Study Design

Type of study design: prospective open controlled clinical trial; Non-random grouping method: According to the exclusion criteria, patients were included into group A or group B according to their wishes after informed consent; Blind level: This experiment is an open study without blind or emergency letters. Research Center: None.

Group A: basic nutrition treatment, energy 30-35 kcal/kg, protein 1.0-2.0 g/kg, diet deficiency, total nutrition and/or whey protein oral nutrition supplement or tube feeding enteral nutrition supplement.

Group B: Since basic nutrition in group A, creatine 5g/d and curcumin 4g/d were orally added, and the intervention time was 1 month.

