It was assumed that after 4 weeks of oral administration of creatine + curcumin in group B, combined with the existing literature on the improvement of the quality of the bad fluid, the skeletal muscle index at L3 section of CT scan in group B was 20% higher than that in control group A, and the standard deviation was 14%. Bilateral test was required, α was 0.05, the sample ratio between the two groups was 1:1 (i.e., the number of cases in the two groups was equal), $\beta=0.2$. The degree of assurance (test efficacy) $1-\beta=80\%$ was calculated using SPSS software, then the sample size of each group was 68 cases, considering the 10% loss of follow-up rate, each group needed 76 cases, 152 patients in total.

Follow-up test item time point

Classification	Item	0	0.5m	1m	3m
Serological indicators	blood routine	√	-	√	√
	biochemical set	√	-	√	√
	prealbumin	√	-	√	√

	transferrin	√	-	√	√
Body composition index	CT scans skeletal muscle index at L3 cross section	√	-	√	√
	BIA measures muscle mass	√	-	√	√
Inflammatory metabolic indicators	Serum insulin	√	-	√	√
	IL-6	√	-	√	√
	TNF- α	√	-	√	√
	lactic acid	√	-	√	√
	PETCT (SUV)	p.r	-	p.r	-
Physical measurements	Weight	√	√	√	√
	grip strength	√	√	√	√
	skin fold thickness	√	√	√	√
	upper arm circumference	√	√	√	√
nutrition assessment	intake	√	√	√	√
	PG-SGA score	√	√	√	√
Questionnaire Survey	Functional Assessment of Anorexia/Cachexia Therapy(FAACT)	√	√	√	√
	ADL evaluation scale	√	√	√	√

4. Criteria

Inclusion Criteria:

(1) Clinical diagnosis of advanced tumors of the upper digestive tract with untreatable or postoperative recurrence of esophageal and gastric cancer III-IV

- (2) Meet the diagnostic criteria of early cachexia (anorexia and metabolic changes, involuntary body mass reduction $\leq 5\%$ within 6 months)
- (3) Radiotherapy, chemotherapy, or immunotherapy in our hospital
- (4) Understand and fill in a variety of rating scales
- (5) Informed consent, voluntary participation in this study

Exclusion Criteria:

- (1) Neoadjuvant chemotherapy patients
- (2) Intestinal obstruction or gastrointestinal bleeding
- (3) Severe heart, lung and renal insufficiency
- (4) Coagulopathy
- (5) Clinical diagnosis with diabetes and other metabolic diseases
- (6) The expected survival time is less than 1 month
- (7) With cognitive dysfunction or poor coordination
- (8) Allergy to creatine or curcumin
- (9) With a history of drug abuse
- (10) Doctors or researchers deem unsuitable for study participation

Removal Criteria:

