- (1) Do not meet the inclusion criteria and mistakenly included or meet any of the exclusion criteria.
- (2) Meet the inclusion criteria but did not use after inclusion or did not have any record of return visit.
- (3) The intervention measures used during the trial did not conform to the protocol.

Criteria for study termination:

- (1) With allergic reactions or serious adverse events should be stopped according to the investigator's judgment.
- (2) Other complications and special physiological changes occurred during the test.
- (3) During the experiment, the subjects needed parenteral nutrition support during the nutritional support process, and the experiment should be stopped.
- (4) Poor compliance.
- (5) Pregnancy.

5. Research methods and technical route

(1) Research food names and specifications

The creatine provided to the patient in this experimental study scheme was purchased from the sports nutrition food Decathlon creatine powder (powder: 10g/ packet *10 packets/box) produced by Jiangsu Alante Nutrition Co., LTD. Purchased from Meriva Curcumin Phytosome (capsule: 1g/ capsule *120 capsules/box) from THORNE Company, USA.

(2) Treatment plan

Clinical data of patients with advanced esophageal and gastric cancer combined with early cachexia were collected, abdominal CT scan was performed, and the skeletal muscle area and

density of L3 section were measured by Matlab software. Skeletal muscle index was obtained after height correction, and body composition and bone mineral density were measured at the same time. Routine examination and nutritional indexes were determined, including blood routine, biochemical set, prealbumin, transferrin; Inflammatory metabolic markers including serum insulin, IL-6, TNF- α , lactic acid, and PETCT were assessed for metabolism. NRS2002 and PG-SGA scores were performed. According to the standard body weight, dietitians formulated diets for all enrolled patients. According to the ESPEN guidelines and the national industry health standard "Dietary Guidelines for Patients with Malignant Tumors 2017", the dietary energy intake standard was 30-35kcal /kg·d, and the protein intake was 1.0-2.0g /kg·d. The deficiency was given to oral enteral nutrition supplements or whey protein supplements, or to patients requiring tube feeding. Patients were enrolled in group A control group or group B intervention group on a voluntary basis.

Group A intervention group: The above basic nutritional support was provided.

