Any adverse events that occur during the test should be recorded in detail.

(1) Large dose of creatine supplement may cause muscle stiffness, spasm and other adverse phenomena.

(2) Exceeding recommended doses of curcumin can cause nausea and even vomiting and diarrhea.

None of the doses used in this study exceeded the recommended dose, so the probability of adverse events was small. Once adverse events occur, the oncologist and nutritionist will be reported immediately, and the current intervention will be suspended according to the actual condition of the patient, and the treatment measures will be developed.

7. Research on quality control and quality assurance

(1) Laboratory quality control measures

The standard operating procedures and quality control procedures for experimental observation indicators should be established in hospital laboratories.

(2) Training of researchers

Prior to the commencement of clinical trials, the investigator should be trained in the protocol.

(3) Measures to improve subject compliance

① The researcher should carefully perform informed consent so that the subjects can fully understand the test requirements and cooperate with the test.

(2) Pay attention to the number of days of experimental drugs, whether there is intermittent drug use, and monitor the compliance of subjects.

Compliance = actual number of days of medication/number of days of medication × 100%

Compliance is 80% ~ 120% compliance is good; Compliance is poor if less than 80% or more than 120%.

(4) Oversight of clinical trials

Monitoring of patients' actual nutrient intake during nutritional therapy:

Follow-up: The patients were discharged from the hospital for routine dietary guidance, with daily total energy set at 30-35kcal /kg.d and daily protein intake at 1.0-2.0 g/kg.d, and continued to receive total nutrition preparations and/or whey protein oral nutrition supplement or tube feeding enteral nutrition supplement.

Monitoring of patients' condition during the experiment:

When the patients included in the study experience changes or even adverse reactions, strict diagnosis and treatment will be taken immediately to avoid the occurrence of adverse events.

8. Data security audit

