The clinical study will develop a data safety monitoring plan according to the risk. All adverse events are recorded in detail, properly handled and tracked until properly resolved or the condition is stable, and serious adverse events and unexpected events are reported to the Ethics Committee, competent authorities, sponsors and drug regulatory authorities in a timely manner in accordance with regulations; The principal investigator conducts regular cumulative reviews of all adverse events and holds investigator meetings where necessary to assess study risks and benefits; For studies with greater than minimum risk, an independent data monitor will be assigned to monitor the study data. For high-risk studies, an independent Data Safety Monitoring committee will be established to monitor the accumulated safety and efficacy data and make recommendations on whether to proceed.

9. Statistical analysis

Statistical analysis was performed using GraphPad Prism version 8.0 (La Jolla, CA, USA). Student's t-test was used for comparison between groups, and one-way analysis of variance (ANOVA) was used for other data. All data are presented as mean \pm SEM. $p < 0.05$ (*) indicates statistical significance. $p < 0.01$ (**) indicates that the difference is more statistically significant.

10. The ethics of clinical research

Clinical research will follow the relevant regulations such as the Declaration of Helsinki of the World Medical Congress. Clinical studies are conducted only after the protocol is approved by the Ethics Committee prior to the start of the study. Before each subject is enrolled in this study, the investigator is responsible to give a complete and comprehensive introduction of the purpose, procedure and possible risks of this study to the subject or his/her agent and sign a written informed consent. Subjects should be informed that they have the right to withdraw from this study at any time, and informed consent should be kept as a clinical study document for future reference. Subjects' privacy and data confidentiality will be protected during the study.

11. Research schedule

Jun 1,2023 to Aug 31,2023: The formal implementation of the project was started. 76 cases were collected, and baseline investigation was conducted for enrolled patients. The patients were not randomly enrolled, and grouped intervention was performed.

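### Enrolled patients can be removed for events after enrolment, and the plan does not say whether their data are analysed; any resulting bias has unknown direction and size

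*Combined protocol and SAP*

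**What the plan says.** Section 4 (Criteria) has three removal criteria. The first is mainly an eligibility check. The other two depend on what happens after enrolment:

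- Criterion 2: "Meet the inclusion criteria but did not use after inclusion or did not have any record of return visit".
- Criterion 3: "The intervention measures used during the trial did not conform to the protocol".

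A separate list in section 4, criteria for study termination, includes "Poor compliance" and the case where "the subjects needed parenteral nutrition support during the nutritional support process, and the experiment should be stopped". Section 7, under measures to improve compliance, gives the threshold: "Compliance is poor if less than 80% or more than 120" percent, calculated from days of medication.

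Section 9 and the statistics row of the Summary describe the analysis only by software, summary format, p thresholds and tests: "t-test was used for comparison between groups, and one-way analysis of variance (ANOVA) was used for other data". Section 3 deals with losses only through the sample size: "considering the 10% loss of follow-up rate, each group needed 76 cases". Groups are not randomised: "patients were included into group A or group B according to their wishes after informed consent".

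**The concern.** No section says whether removed or terminated patients stay in the analysis, or what happens when a 4-week value is missing. If removal means removal from the analysis, the t-test compares patients selected by their conduct and course after enrolment.

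That selection need not be the same in both groups. Criterion 3 and the parenteral nutrition rule can apply to either group. The compliance ratio counts days of the experimental product, which only group B takes. Removal could therefore differ by group, although the documents do not show that it will.

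Removal may also be linked to prognosis. In advanced cancer, failing to return or needing parenteral nutrition can reflect deterioration. A patient who dies before any return visit could meet criterion 2 and drop out of the count, although 1- and 3-month survival is a listed secondary indicator. Section 5 collects survival by telephone, but the plan does not say whether a call counts as a return visit. So the gap affects survival as well as the L3 skeletal muscle index and the other indicators.

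**Working it through.** **The plan's own figure.** Section 3 has 68 per group, inflated for 10% loss: 68 / (1 - 0.10) = 75.6, rounded up to 76, and 2 x 76 = 152. This step reproduces. It only enlarges the sample and does not say who is analysed. (Whether 68 follows from the stated effect and SD is a separate matter and is not used here.)

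**Inputs for the illustration.** From the documents: 76 enrolled per group and two-sided alpha 0.05 (section 3). Assumed, because the documents give no removal rate and no link between removal and outcome:

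- removed share q of 10%, 20% or 30%;
- the patients lowest on a trait such as adherence or fitness are removed;
- the trait has correlation r with the outcome, with |r| = 0.1 to 0.5;
- no true effect, and groups comparable at enrolment.

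**Formulas, per group.** Let z be the standard normal q-quantile and lambda = phi(z)/(1 - q).

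- Mean shift = r x lambda.
- Variance = 1 - r² x (lambda² - z x lambda).
- n = 76 x (1 - q).
- The difference B minus A is tested by a two-sided z-test.

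Lambda is 0.195 at q = 10%, 0.350 at 20% and 0.497 at 30%.

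**One case in full: A 10%, B 30%, r = 0.5.**

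- Shift = 0.5 x (0.497 - 0.195) = 0.151 SD.
- Variances are 0.928 and 0.873; n = 68.4 and 53.2.
- SE = sqrt(0.928/68.4 + 0.873/53.2) = 0.173, and 0.151/0.173 = 0.87.
- Rejection probability = P(Z > 1.96 - 0.87) + P(Z < -1.96 - 0.87) = 14.0%.

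**All cases.**

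| Removed A / B | Shift in SD, r = 0.1 / 0.2 / 0.3 / 0.5 | Type I error |
|---|---|---|
| 10% / 10% | 0 throughout | 5.0% throughout |
| 10% / 20% | 0.015 / 0.031 / 0.046 / 0.077 | 5.1 / 5.4 / 5.8 / 7.5% |
| 10% / 30% | 0.030 / 0.060 / 0.091 / 0.151 | 5.3 / 6.3 / 8.0 / 14.0% |
| 20% / 10% | same sizes as 10% / 20%, negative | as 10% / 20% |
| 30% / 10% | same sizes as 10% / 30%, negative | as 10% / 30% |

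A simulation with the pooled t-test (40,000 trials) agrees at r = 0.5: 7.6% for 10%/20% and 13.8% for 10%/30%.

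**Sign.** Positive r means that those removed would have done worse, so heavier removal in B favours the supplement. With negative r the sign reverses: A 10%, B 30% gives -0.09 SD at r = -0.3 and -0.15 SD at r = -0.5. The model removes one tail only, whereas the compliance band has two sides, so the table shows scale and is not a prediction.

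**The case against.** **Removal may not mean removal from the analysis.** This stands in part. Neither list is tied to the analysis, so the documents do not show that the data will be discarded. They also do not show that the data will be kept, and that is the gap. For patients with no return visit, no post-baseline visit outcome exists under any analysis set, so that part of criterion 2 is mainly a missing-data question.

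**The illustrated bias is mostly small.** This stands. With A 10%, B 20% and r up to 0.3, type I error is at most 5.8%. The largest shift shown, 0.15 SD, compares with a planned effect of 20/14 = 1.43 SD, and with about 0.48 SD detectable at 80% power with 68 per group ((1.96 + 0.84) x sqrt(2/68)). The true effect is unknown, however, and the gap affects every indicator.

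**Self-selection may matter more.** This also stands. The 5.0% reference assumes comparable groups, which allocation by patient wish does not secure.

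**Stronger readings that the documents do not support.**

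- A reader might infer that the rules tilt the result towards the supplement. That needs heavier removal in B and worse outcomes in those removed; neither is established.
- A reader might assume no removal in A at all. Several rules reach A, so that is not a fair scenario.
- A reader might infer from section 11, which plans an analysis of early patients and then changes to the program, that the analysis set will be chosen after results are seen. Section 11 mentions neither removal rules nor analysis sets.

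**Conclusion.** The point holds as a correctable weakness in the analysis plan. Criteria 2 and 3 and parts of the termination list act on post-enrolment events, and nothing in sections 4 or 9 or the Summary keeps these patients in a defined analysis set or says how missing values are handled.

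Bias arises only if their data are left out, removal is related to outcome, and removal differs by group. Under the assumed values the shift is 0.02-0.15 SD in either direction, with type I error of 5.1-14.0%. It is zero if removal is equal and works by the same mechanism. The removal rates and correlations are assumptions, so actual direction and size remain unknown. The change should be made, with medium confidence that it will matter in practice.

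**What to change.** 1. Make the primary analysis all eligible enrolled patients, in the group chosen at enrolment, whatever their adherence. Exclude only for ineligibility on facts that existed before enrolment, judged the same way in both groups.
2. Use removal criteria 2 and 3 only to define a per-protocol sensitivity set. The 80-120% band counts days of experimental product and so screens only group B. Either define conformity by criteria that apply to both groups, or state the asymmetry and do not read that set as an unbiased comparison.
3. Keep all data already collected. For patients who stop the intervention, continue the follow-up already scheduled only where it remains permitted and consented to. State how study termination in section 4 relates to further data collection. The clinical stopping rules stay unchanged.
4. Report removals, terminations and deaths by group with reasons. Count deaths in the planned 1- and 3-month survival rates even if there was no return visit, and do not impute muscle values after death.
5. Before the final analysis, state one baseline-adjusted missing-data method. Add a sensitivity analysis that varies the missing values in both groups and in both directions, and reports where the conclusion changes. Give the number of patients with baseline data only, by group.

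The cost is protocol and SAP wording, some follow-up at visits already scheduled, and a little more analysis. The estimate may be smaller than the per-protocol one. The change avoids adding selection after enrolment; it does not remove confounding from patient-chosen groups.

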Group B control group: In addition to the above basic nutrition, oral creatine powder 5g qd, curcumin capsule 2g bid for one month.

The intake, complications and survival of the patients were followed up by telephone for 1 and 3 weeks, physical indicators, nutritional assessment, FAACT and QoL scale were followed up for 2 weeks in the hospital and outpatient department, and nutritional serum indicators, body composition indicators, inflammatory metabolism indicators, physical indicators, nutritional assessment were reviewed for 4 weeks. Evaluation of effect. The long-term survival, re-hospitalization and hospitalization expenses were investigated 3 months later. To evaluate the effect of creatine combined with curcumin on improving the nutritional status, metabolic level and clinical prognosis of alimentary tract neoplasm. Note: Weight is calculated by standard weight: Standard weight (kg) = height (cm)-105.

(3) Combination of drugs

During the study period, patients may have been treated with chemotherapy drugs and immunotherapy drugs due to tumor treatment and may have taken megestrol orally against the oxalic fluid to improve appetite. To avoid the influence of the two groups of therapeutic drugs, the diseases, and drugs of the two groups will eventually be grouped and stratified to eliminate the interference of combined drug use.

(4) Safety evaluation index

- ① Incidence and severity of side effects
- ② The rate of unplanned rehospitalization.

6. Observation of adverse events

Adverse Event (Adverse Event): An adverse medical event occurs after a patient or clinical trial subject receives a drug or a formula for a special medical use, but there is not necessarily a causal relationship.

Serious Adverse Event: An event occurs during the clinical trial that requires hospitalization, prolongates the hospital stay, causes disability, affects the ability to work, threatens life or death, or

results in congenital malformations.

Adverse reaction: an adverse reaction that is harmful rather than expected but is causally related to the application of a drug or special medical use formula food during normal application of the drug or special medical use formula food at prescribed doses. In clinical trials for a new use, all reactions that are harmful and not causally related to the use of a drug or a formula for special medical use, as expected, should be considered adverse when the dose has not been determined.

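### The protein target can vary twofold within the protocol and need not be fixed before the patient chooses a group, and no planned analysis accounts for diet, so a diet difference would be read as a supplement effect

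*Combined protocol and SAP*

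**What the plan says.** All references are to the combined protocol and SAP.

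- **Background nutrition.** Both groups get the same basic nutrition, and group B adds creatine and curcumin (sections 3(1) and 5(2)). Under section 5(2), "dietitians formulated diets for all enrolled patients"; "the dietary energy intake standard was 30-35kcal /kg·d", and "the protein intake was 1.0-2.0g /kg·d".
- **Weight basis.** "Weight is calculated by standard weight: Standard weight (kg) = height (cm)-105" (section 5(2)).
- **Shortfall.** "The deficiency was given to oral enteral nutrition supplements or whey protein supplements", with tube feeding where it is required (section 5(2)). No rule is given for the amount, or for where a patient sits in the range.
- **After discharge.** Section 7(4) restates the ranges: "daily total energy set at 30-35kcal /kg.d and daily protein intake at 1.0-2.0 g/kg.d".
- **Allocation and blinding.** Patients join a group by their own wish. "This experiment is an open study without blind or emergency letters" (section 3(1)).
- **Order of steps.** Section 5(2) mentions the diets before it mentions group entry. The Summary and section 3(1) describe nutrition as part of each group's treatment. Neither order is stated as a rule.
- **Intake data.** Energy and protein intake is a secondary indicator (Summary), scheduled at 0, 0.5, 1 and 3 months (schedule in section 3).
- **Analysis.** Section 9 gives Student's t-test between groups and one-way ANOVA for other data, with no covariates. Section 5(3) plans to stratify by diseases and drugs.

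**The concern.** The intended contrast is the same basic nutrition with or without the supplements. That holds only if nutrition is in fact the same on average in the two groups. Here one component has a permitted range whose top is twice its bottom, a professional chooses the value, and nothing stops that choice being made with the group known.

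The protocol's safeguards do not reach this. The removal criterion for interventions that depart from the protocol (section 4) cannot detect a group difference in diet, because every value in the range conforms. Section 5(3) recognises that co-treatment may differ between groups and plans stratification for it, but has no counterpart for diet. The t-test attributes the whole difference in means to group membership.

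The L3 skeletal muscle index is the endpoint used to size the trial, and the protocol treats nutrition as the basic treatment of cachexia (sections 1.1 and 1.2.2). If group B were fed nearer the top of the range than group A, the muscle comparison would mix the two causes. The reverse pattern could hide a real effect.

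**Working it through.** **1. The plan's own sample size.** Inputs from section 3: difference 20%, SD 14%, two-sided alpha 0.05, power 80%, ratio 1:1.

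n per group = 2 × (1.96 + 0.84)² × (14/20)² = 2 × 7.84 × 0.49 = 7.7, so 8 (9 with the t distribution). The stated 68 is not reproduced. The dropout step is: 68/0.90 = 75.6, so 76 per group and 152 in total. The present point does not depend on this mismatch. I use 68 and 14% below only because they are the plan's stated values.

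**2. What the range permits.** Protein: 2.0/1.0 = a factor of 2. Energy: 35/30 = 1.17. Standard weight is height minus 105; the heights are assumed.

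| Height (cm) | Standard weight (kg) | Protein on protocol (g/d) |
|---|---|---|
| 155 | 50 | 50-100 |
| 165 | 60 | 60-120 |
| 175 | 70 | 70-140 |

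These are limits for single patients. They show the room for a group difference and do not estimate one.

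**3. What a diet-driven shift would do to the t-test.** Suppose the supplements do nothing and diet moves the group means apart by b percentage points of muscle index. I assume that the stated SD applies to the quantity compared.

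SE = 14 × √(2/68) = 2.40

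P(p<0.05) = 1 − Φ(1.96 − b/SE) + Φ(−1.96 − b/SE)

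For b = 3: 3/2.40 = 1.25; 1 − Φ(0.71) = 0.239; the second term is below 0.001; total 0.24.

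| Assumed shift b (points) | Chance of p<0.05 |
|---|---|
| 0 | 5% |
| 1 | 7% |
| 2 | 13% |
| 3 | 24% |
| 5 | 55% |

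**4. From a protein gap to a shift.** The documents give no effect of protein on muscle index. Over an assumed range of slopes, b = gap × slope:

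| Gap between group means (g/kg/d) | Slope 2 points per g/kg/d | Slope 5 | Slope 10 |
|---|---|---|---|
| 0.25 | b = 0.5; 5.5% | b = 1.25; 8% | b = 2.5; 18% |
| 0.50 | b = 1.0; 7% | b = 2.5; 18% | b = 5.0; 55% |

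The result runs from negligible to serious, and the documents cannot say where in that range the trial would fall.

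**The case against.** The case on the other side has real weight.

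- **Individualised targets are ordinary practice.** Both groups share one nominal standard, which section 5(2) attributes to guidelines. That is correct: the range is not an error, and the issue is only that its use is not protected from knowledge of the group.
- **Intake is measured.** It is scheduled four times and followed by telephone at weeks 1 and 3 (section 5(2)), so an imbalance would be visible. This stands and narrows the point. But no analysis uses the data, and intake after baseline may itself respond to treatment.
- **The protocol doubts that feeding builds muscle here.** Section 1.1 says that patients often fail to respond even to ample energy and protein. This argues for a small effect without excluding one, and is a reason to leave the size open.
- **The shifts illustrated are well below the 20% planned for.** True, but section 9 judges success by p<0.05. With SD 14% and 68 per group, a difference of about 6.8 points already has 80% power.
- **Self-selection is the larger problem.** Patients who choose supplements may differ in appetite and motivation under identical targets. This stands, and the fix below does not cure it.

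A reader might infer that dietitians revise targets during follow-up with the group known. The documents do not say so: they say that diets are formulated, shortfalls are supplemented and the same ranges are restated at discharge. A reader might also take the gap between two patients at opposite ends of the range, or a comparison of grams of protein with grams of supplement, as a measure of bias. Neither is a group difference, and neither translates into muscle index.

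**Conclusion.** The point holds as a gap in procedure and analysis. Targets may be set with the group known, they may differ twofold within the protocol, and nothing planned accounts for diet. Bias is possible and is not shown; the documents do not support saying that the groups will be fed differently.

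Its size cannot be computed. The 7%, 24% and 55% for shifts of 1, 3 and 5 points rest on the plan's SD of 14% and 68 per group, a normal approximation, no supplement effect, and shifts that I have assumed. A modest gap with a weak protein effect leaves the error rate close to 5%. The point merits a change because the remedy is cheap and must be in place before patients choose.

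**What to change.** - **Procedure (section 5(2)).** State that each patient's energy and protein target is entered in the record before the patient states a group. Log later changes, with date and reason.
- **Analysis (section 9).** For muscle index and weight, replace the unadjusted t-test with ANCOVA: group, baseline value of the outcome, pre-choice protein target, and the baseline intake already collected.
- **Reporting.** Tabulate prescribed targets, and actual intake at 0, 0.5, 1 and 3 months, by group. Use post-baseline intake descriptively or in a sensitivity analysis only. Treatment may affect it (the Summary and section 6 note nausea, vomiting and diarrhoea with large curcumin doses), so adjusting for it in the main model could remove part of the effect or add bias.

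The cost is one form field, a change log, and a little more analysis, with no extra visits. The covariates use few degrees of freedom against 2 × 68 = 136 patients.

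The limits should be stated in the plan: a pre-choice target cannot correct divergence after the choice, and no covariate set removes the confounding from patient-chosen groups. No nutritional target is proposed here; that is for the clinical team.
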